9.3 Hy's Law

Cases where a patient shows elevations in liver biochemistry may require further evaluation and occurrences of AST or ALT $\geq 3 \times$ ULN together with total bilirubin $\geq 2 \times$ ULN may need to be reported as SAEs. Please refer to Appendix 1 for further instruction on cases of increases in liver biochemistry and evaluation of Hy's law.

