
Design
	
Design
  
Control arm: no treatment. Crossover to Regorafenib + Durvalumab upon relapse Experimental arm: Regorafenib 90mg d1-21 q28 + Durvalumab 1500mg (Q4W) up to 1 year

Run-in phase
	
The combination of an immune-checkpoint inhibitor plus TKI anti-angiogenic agents has been extensively investigated in several trials (phase II and III) in different types of tumors, with no evidence of new safety signals. Although specific data are not available on the combination of durvalumab and regorafenib, we would not expect major toxicity issues.
 
The run-in phase will be conducted on the first 4 patients randomized to the experimental arm using a starting dose of 60 mg/die of Regorafenib (and fixed 1500 mg of Durvalumab), to be escalated after 2 months to 90 mg/die if < 2 patients report serious adverse events (SAE). If Regorafenib 90 mg/die is well tolerated for other 2 months (< 2 patients with SAE) the run-in phase will be closed with the dose of 90 mg/die. In case of > 2 patients report SAE with 90 mg/die, additional 4 patients will be enrolled and treated with the same dose of Regorafenib (90 mg/die) and if < 2 of them report SAE the run-in will be closed at 90 mg/die. Conversely, if > 2 patients report SAE the dose of Regorafenib will be reduced again to 60 mg/die and the run-in will be closed with Regorafenib 60 mg/die.
 
If during the first part of the run-in > 2 patients report SAE with Regorafenib 60 mg/die, additional 4 patients will be treated with Regorafenib 30 mg/die for 2 months and, in case of > 2 patients with SAE, the trial will be revised. In case of good tolerance of Regorafenib 30 mg/die (< 2 patients with SAE), additional 4 patients will be enrolled and treated with Regorafenib 60 mg/die: if > 2 patients will report SAE the run-in phase will be closed with Regorafenib 30 mg/die, instead if Regorafenib 60 mg/die will be well tolerated (< 2 SAE) this will be the final dose of the run-in phase.

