4.3 Study plan

Approximately 182 patients, >18 years of age, with Stage IV CRC and no evidence of disease (NED) will be enrolled. Randomization will be 1:1.

Prior to enrolment, all patients will have received standard of care (SoC) treatment for Stage IV CRC (locoregional), and will have to be NED.

Treatment schedules and safety and efficacy assessments will be the same for all patients, regardless of treatment group.

All patients will undergo assessments (Section 6.2) to confirm compliance with inclusion and exclusion criteria, after that they will sign informed consent. Patients who will be randomized to the experimental treatment group will receive up to 1 year of regorafenib plus durvalumab.

Run-in phase: The combination of an immune-checkpoint inhibitor plus TKI anti-angiogenic agents has been extensively investigated in several trials (phase II and III) in different types of tumors, with no evidence of new safety signals. Although specific data are not available on the combination of durvalumab and regorafenib, we would not expect major toxicity issues.

Therefore, a run-in phase will be conducted on the first 4 patients randomized to the experimental arm using a starting dose of 60 mg/die of Regorafenib (and fixed 1500 mg of Durvalumab), to be escalated after 2 months to 90 mg/die if < 2 patients report serious adverse events (SAE). If Regorafenib 90 mg/die is well tolerated for other 2 months (< 2 patients with SAE) the run-in phase will be closed with the dose of 90 mg/die. In case of > 2 patients report SAE with 90 mg/die, additional 4 patients will be enrolled and treated with the same dose of Regorafenib (90 mg/die) and if < 2 of them report SAE the run-in will be closed at 90 mg/die. Conversely, if > 2 patients report SAE the dose of Regorafenib will be reduced again to 60 mg/die and the run-in will be closed with Regorafenib 60 mg/die.

If during the first part of the run-in > 2 patients report SAE with Regorafenib 60 mg/die, additional 4 patients will be treated with Regorafenib 30 mg/die for 2 months and, in case of > 2 patients with SAE, the trial will be revised. In case of good tolerance of Regorafenib 30 mg/die (< 2 patients with SAE), additional 4 patients will be enrolled and treated with Regorafenib 60 mg/die: if > 2 patients will report SAE the run-in phase will be closed with Regorafenib 30 mg/die, instead if Regorafenib 60 mg/die will be well tolerated (< 2 SAE) this will be the final dose of the run-in phase.

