7.1.1 Run-in phase

Run-in phase: The combination of an immune-checkpoint inhibitor plus TKI anti-angiogenic agents has been extensively investigated in several trials (phase II and III) in different types of tumors, with no evidence of new safety signals. Although specific data are not available on the combination of durvalumab and regorafenib, we would not expect major toxicity issues.

Therefore, a run-in phase will be conducted on the first 4 patients randomized to the experimental arm using a starting dose of 60 mg/die of Regorafenib (and fixed 1500 mg of Durvalumab), to be escalated after 2 months to 90 mg/die if < 2 patients report serious adverse events (SAE). If Regorafenib 90 mg/die is well tolerated for other 2 months (< 2 patients with SAE) the run-in phase will be closed with the dose of 90 mg/die. In case of > 2 patients report SAE with 90 mg/die, additional 4 patients will be enrolled and treated with the same dose of Regorafenib (90 mg/die) and if < 2 of them report SAE the run-in will be closed at 90 mg/die. Conversely, if > 2 patients report SAE the dose of Regorafenib will be reduced again to 60 mg/die and the run-in will be closed with Regorafenib 60 mg/die.

If during the first part of the run-in > 2 patients report SAE with Regorafenib 60 mg/die, additional 4 patients will be treated with Regorafenib 30 mg/die for 2 months and, in case of > 2 patients with SAE, the trial will be revised. In case of good tolerance of Regorafenib 30 mg/die (< 2 patients with SAE), additional 4 patients will be enrolled and treated with Regorafenib 60 mg/die: if > 2 patients will report SAE the run-in phase will be closed with Regorafenib 30 mg/die, instead if Regorafenib 60 mg/die will be well tolerated (< 2 SAE) this will be the final dose of the run-in phase.

(see Flowchart in Appendix 4)

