7.4 Dose-limiting toxicities (DLTs)

A DLT is defined as the occurrence of an adverse event (AE) that is at least possibly related to the investigational product (IP) or investigational regimen (IR), with two exceptions: any grade of vitiligo or alopecia will not qualify as a DLT. AEs that are at least possibly related to durvalumab- and/or tremelimumab-containing regimens shall be assessed as DLTs if they meet any of the following criteria:

Hematologic toxicity:

- Grade ≥ 3 neutropenia complicated by fever $>38.3^{\circ}\text{C}$
- Grade 4 neutropenia (lasting more than 7 days)
- Grade ≥ 3 thrombocytopenia with significant bleeding
- Grade 4 thrombocytopenia (regardless of duration)
- Grade 4 anemia (regardless of duration)

Non-hematologic toxicity:

- Any Grade 4 non-immune-mediated AE
- Any Grade 4 immune-mediated AE, excluding endocrinopathies
- Any Grade 3 non-immune mediated AE that does not resolve to \leq Grade 1 or baseline within 30 days with optimal medical management
- Any Grade 3 immune-mediated AE – excluding diarrhea/colitis, pneumonitis, hepatitis, rash, neurotoxicity, myocarditis, myositis/polymyositis, endocrinopathies and nephritis – that does not resolve to \leq Grade 1 or baseline within 30 days after onset of the event despite optimal medical management including systemic corticosteroids

- Grade 3 diarrhea or colitis that does not resolve to \leq Grade 1 within 14 days [both immune- and non-immune-mediated indicated here; the same is the case if not specified in remaining bullet points below]
- Grade 3 non-infectious pneumonitis
- Grade 2 noninfectious pneumonitis that does not resolve to \leq Grade 1 within 3 days of the initiation of maximal supportive care
- Aspartate aminotransferase (AST) or alanine aminotransferase (ALT) $\geq 3 \times$ ULN with concurrent increase in total bilirubin (TBL) $\geq 2 \times$ ULN without evidence of cholestasis or alternative explanations (e.g., viral hepatitis, disease progression in the liver; i.e., “Hy’s Law”)
- ALT or AST $> 8 \times$ ULN or TBL $> 5 \times$ ULN
- Grade 3 immune-mediated rash that does not resolve to \leq Grade 1 or baseline within 30 days
- Grade 2 rash covering $> 30\%$ BSA that does not resolve to \leq Grade 1 or baseline within 30 days
- Any grade of immune-mediated rash with bullous formation
- Grade 3 immune-mediated neurotoxicity (excluding Guillain-Barre and myasthenia gravis) that does not resolve to \leq Grade 1 within 30 days

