- Grade 2 or 3 immune-mediated peripheral neuromotor syndrome (such as Guillain-Barre and myasthenia gravis) that does not resolve to \leq Grade 1 within 30 days or that exhibits signs of respiratory insufficiency or autonomic instability
- Grade 3 immune-mediated myocarditis
- Any symptomatic immune-mediated myocarditis that does not become asymptomatic within 3 days of initiating optimal medical management including systemic corticosteroids
- Grade 2 or 3 immune-mediated myositis/polymyositis that does not resolve to Grade ≤ 1 within 30 days of initiating optimal medical management including systemic corticosteroids or that exhibits signs of respiratory insufficiency regardless of optimal medical management
- Immune-mediated increase in creatinine $> 3 \times$ ULN, or $> 3 \times$ baseline for patients with a baseline creatinine elevated above ULN

The period for evaluating DLTs will be from the time of first administration of durvalumab until the complete resolution of the treatment-related toxicity.

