
Abbreviations: BP=blood pressure; CTCAE=common terminology criteria for adverse events; G=Grade; Hg=mercury
 
If reductions are required resulting in a daily dose of less than 30 mg of regorafenib, regorafenib will be permanently discontinued. If BP remains controlled for at least one full cycle, dose re-escalation is permitted at the Investigator's discretion. Patients requiring a delay of > 4 weeks (28 days) (including the 1 week drug holiday) should discontinue regorafenib treatment. However, continuation of regorafenib may be considered if, in the Investigator's opinion, the patient may continue to benefit from the regorafenib treatment, and after consultation with the Medical Monitor.
	

Regorafenib Dose Modification Guidance, Non-Immune Toxicities: Liver Function Test Abnormalities^a

Increases in AST/ALT and/or bilirubin	1 st occurrence	Restart	Recurrence
AST and/or ALT ≤ to 5 x ULN, with normal AST and/or ALT at baseline	Continue dosing , with weekly monitoring of liver function until transaminases return to < 3 x ULN (< or equal to G1) or baseline.		
AST and/or ALT > 5 x ULN	Interrupt dosing , with weekly monitoring of liver function until transaminases return to < 3 x ULN or baseline.	If the potential to reinitiate regorafenib is considered to outweigh the risk of hepatotoxicity: reduce 1 dose level and measure serum transaminases weekly for at least 4 weeks.	Discontinue permanently
AST and/or ALT > 20 x ULN	Discontinue permanently and measure serum transaminases weekly until resolution.		

AST and/or ALT > 3 x ULN with concurrent total bilirubin > 2 x ULN	Discontinue permanently and measure serum transaminases weekly until resolution. Exception: participants with Gilbert's syndrome who develop elevated transaminases should be managed as per the above outlined recommendations for the respective observed elevation of ALT and/or AST.		

Abbreviations: ALT=alanine aminotransferase; AST=aspartate aminotransferase; ULN=upper limit of normal; G=Grade
 
If reductions are required resulting in a daily dose of less than 30 mg of regorafenib, regorafenib will be permanently discontinued.
 
Footnote:
 
a) If all values remain stable for 2 full cycles, dose re-escalation may be considered at the discretion of the Investigator. After re-escalation AST, ALT, bilirubin should be checked 2x/week for 2 weeks, followed by weekly assessments for at least 4 weeks.
			

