9.7.2 Hepatic function abnormality

Hepatic function abnormality that fulfills the biochemical criteria of a potential Hy's Law case in a study patient, with or without associated clinical manifestations, is required to be reported as "hepatic function abnormal" within 24 hours of knowledge of the event to the sponsor. The criteria for a potential Hy's Law case is Aspartate Aminotransferase (AST) or Alanine Aminotransferase (ALT) $\geq 3x$ Upper Limit of Normal (ULN) together with Total Bilirubin (TBL) $\geq 2x$ ULN at any point during the study following the start of study medication irrespective of an increase in Alkaline Phosphatase (ALP).

- If the definitive underlying diagnosis for the abnormality has been established and is unrelated to investigational product, the decision to continue dosing of the study patient will be based on the clinical judgment of the investigator.
- If no definitive underlying diagnosis for the abnormality is established, dosing of the study patient must be interrupted immediately. Follow-up

investigations and inquiries must be initiated by the investigational site without delay.

Each reported event of hepatic function abnormality will be followed by the investigator and evaluated by the sponsor.

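### A confirmed Hy's Law case is not guaranteed to enter the SAE count that steers the run-in dose, and the rule states no action at exactly 2 of 4 patients

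*Combined protocol and SAP*

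**What the plan says.** **Run-in rule.** Section 4.3 starts the first 4 experimental-arm patients on regorafenib 60 mg, "to be escalated after 2 months to 90 mg/die if < 2 patients report serious adverse events (SAE"). The synopsis uses the same criterion ("if < 2 patients report serious adverse events (SAE"), and so does 7.1.1. The adverse branch begins "If during the first part of the run-in > 2 patients report SAE with Regorafenib 60 mg/die". All five decision points use this pair of conditions: fewer than 2, or more than 2.

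**SAE status of a Hy's Law case.** Section 9.3 says that AST or ALT at least 3 x ULN together with bilirubin at least 2 x ULN "may need to be reported as SAEs. Please refer to Appendix 1 for further instruction on cases of increases in liver biochemistry". Section 7.4.5 is equally permissive, and joins the two laboratory limits with *or*. Section 9.7.2 ("Hepatic function abnormality that fulfills the biochemical criteria of a potential" Hy's Law case) requires a report to the sponsor within 24 hours and evaluation by the sponsor. It sits under other events requiring reporting and does not call the case an SAE.

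**Consequence for the patient.** Section 7.4 lists the case as a DLT when it occurs "without evidence of cholestasis or alternative explanations". The liver table in 7.5.1 stops regorafenib permanently at "AST and/or ALT > 3 x ULN with concurrent total bilirubin > 2 x ULN", except in Gilbert's syndrome. Appendix 3 permanently stops the study drug or regimen for a Hy's Law case without cholestasis or another cause.

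**The concern.** The run-in exists because, in the words of 4.3 paraphrased, specific data on this combination are lacking. It is a count of 4 patients, so one patient can change the decision. A confirmed Hy's Law case is among the clearest signs that a dose is not tolerated, yet whether it enters the count depends on how the investigator classifies it. Two such patients, or one alongside one patient with another SAE, could leave the count below 2 and meet the written condition for escalation.

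The second problem is independent of the liver. With exactly 2 of 4 patients counted, the escalation condition is not met and the adverse branch is not triggered. The readable text then gives the site no instruction. The two problems meet in the most natural example: one SAE plus one counted Hy's Law case makes exactly 2.

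**Working it through.** The plan states no operating characteristic for the run-in, so there is no figure to reproduce.

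**1. Can a confirmed case stay out of the count?** Three places bear on this.
- 9.3 and 7.4.5 are permissive. By contrast, 9.4 says directly that a new cancer should be treated as an SAE.
- 9.7.6 makes a laboratory abnormality an SAE only if it meets SAE criteria. The medically significant criterion in 9.1.3 is left to judgement.
- By the Appendix 3 limits, ALT of 3 to 5 x ULN with bilirubin of 2 to 3 x ULN is Grade 2, with no instruction to hospitalise. No other SAE criterion is met automatically.

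So it can stay out, although nothing says that it should.

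**2. Effect on the count, if Hy's Law cases are filed only under 9.7.2**

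| Other-SAE patients | Hy's Law patients | Count as filed | Count if included |
|---|---|---|---|
| 1 | 1 | 1: escalate | 2: no written action |
| 0 | 2 | 0: escalate | 2: no written action |
| 2 | 1 | 2: no written action | 3: adverse branch |

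**3. Probability of a miscount at the 60 mg step.** All three inputs are assumptions.
- s: risk of another SAE per patient. The base value of 6.5% is the durvalumab monotherapy related-SAE rate in 2.9.5.1; it is neither a 2-month rate nor a rate for the combination.
- h: Hy's Law risk per patient over 2 months. The documents give none, so 1% to 10% is shown.
- q: share of Hy's Law cases filed as SAEs.

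Per patient, P(counted) = C = 1 - (1 - s)(1 - hq), and P(Hy's Law only, not counted) = U = (1 - s)h(1 - q). For 4 patients (trinomial), miscount = P(number counted < 2 and number counted or uncounted >= 2).

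Example with s = 0.065, h = 0.05, q = 0: C = 0.065, U = 0.935 x 0.05 = 0.04675, C + U = 0.11175. P(counted >= 2) = 0.0232 and P(counted or uncounted >= 2) = 0.0642. The miscount is 0.0642 - 0.0232 = 0.0410.

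| s | q | h = 1% | 3% | 5% | 10% |
|---|---|---|---|---|---|
| 6.5% | 0 | 0.7% | 2.3% | 4.1% | 9.8% |
| 6.5% | 0.5 | 0.4% (0.0035) | 1.2% | 2.3% | 5.7% |
| 6.5% | 0.8 | 0.1% | 0.5% | 1.0% | 2.4% |
| 15% | 0 | 1.1% | 3.5% | 6.0% | 12.7% |
| 15% | 0.5 | 0.6% | 1.8% | 3.1% | 6.7% |

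**4. The gap at exactly 2.** With per-patient SAE risk p, P(exactly 2 of 4) = 6p²(1 - p)² and P(more than 2) = 4p³(1 - p) + p⁴.

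| p | exactly 2 | more than 2 |
|---|---|---|
| 6.5% | 2.2% | 0.1% |
| 10% | 4.9% | 0.4% |
| 20% | 15.4% | 2.7% |
| 30% | 26.5% | 8.4% |

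At every value shown, the outcome without an instruction is likelier than the outcome with one.

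**The case against.** The strongest reply is that SAE classification is likely in practice. Section 9.1.3 counts any medically significant event. Appendix 3 places the Hy's Law stop in its Grade 3 or 4 row, where management is prompt intravenous methylprednisolone. Section 9.7.2 has the sponsor evaluate every case and interrupts dosing at once if no diagnosis is established. The set in 9.3 and 9.7.2 is also wider than the confirmed case in 7.4 and Appendix 3, because it excludes neither cholestasis nor another cause; permissive wording is reasonable for cases still being worked up. All of this stands. It makes a miscount less likely, but none of it puts a confirmed case into the count.

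Three stronger readings are tempting, and the documents do not support them.
- *That a miscount at 60 mg sets the dose for the remaining 87 of 91 planned experimental-arm patients (91 - 4).* It does not. The 90 mg dose must pass a further 2-month check before the run-in closes, and later patients can be reduced to 60 or 30 mg. The check has a limit of its own: a patient permanently off treatment contributes nothing at 90 mg, and the text does not mention replacement.
- *That the affected patient is left on treatment.* The stopping rules in 7.5.1 and Appendix 3 apply whatever the SAE status.
- *That the rule must count every DLT in 7.4.* Choosing SAEs is a defensible design. An SAE needs no causal link, whereas a DLT must be at least possibly related. The list in 7.4 also names tremelimumab, and its window is open-ended: "The period for evaluating DLTs will be from the time of first administration of durvalumab until the complete resolution of the treatment-related toxicity".

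On exactly 2, one may say that any reader would decline to escalate. That is right, but the rule still does not say whether to expand, reduce or continue.

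**Conclusion.** Both parts hold on the readable text. A confirmed Hy's Law case is not guaranteed to enter the run-in count, so the written rule can permit escalation although 2 or more of 4 patients had an SAE or such a case. The probability cannot be estimated from the documents. Under the assumptions above it is small unless the liver risk is high: about 2% or less at a 3% Hy's Law risk with 6.5% other SAEs, and nearly 10% only if the risk is 10% and no case is filed as an SAE. Closing this gap is a cheap improvement. The missing action at exactly 2 is wrong as written and needs no assumption to establish.

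The DFS analysis and the toxicity analysis by CTCAE grade are unaffected. The Safety Management Plan and the Appendix 4 flowchart were not available for this review; either could already settle one of these points, in which case the protocol text needs only to be aligned with it.

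**What to change.** 1. In 9.3 and 7.4.5, state that AST or ALT >= 3 x ULN together with bilirubin >= 2 x ULN is reported as an SAE (important medical event) within 24 hours, unless a definite unrelated cause is documented, and that it counts in the run-in.
2. In the synopsis, 4.3, 7.1.1 and the Appendix 4 flowchart, change each > 2 to >= 2. Item 1 is incomplete without this, because one SAE plus one Hy's Law case would still have no stated action.
3. In 9.3, correct the reference to Appendix 1 (the ECOG scale) to Appendix 3. This is clerical; 9.1.2 makes the same slip while naming the toxicity guidelines.

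**Cost.** A short amendment and a line of SAE-form guidance; no change to sample size, visits or primary analysis. The run-in becomes slightly more likely to stay at or return to a lower dose. With s = 6.5% and no case otherwise filed as an SAE, the chance that the 60 mg escalation condition is not met rises from 2.3% to 3.0%, 4.6%, 6.4% or 12.1% at h = 1%, 3%, 5% or 10%.

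**Optional.** The sponsor may consider counting the other DLTs in 7.4 as well. Some of them can be called only after 30 days without resolution, so escalation could wait up to about a month. The documents do not allow the effect on the dose decision to be estimated, and this is not part of the required change.

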9.4 New cancers

The development of a new cancer should be regarded as an SAE. New primary cancers are those that are not the primary reason for the administration of the IP and have been identified after the patient's inclusion in this study.

9.5 Deaths

All deaths that occur during the study treatment period, or within the protocol-defined follow-up period after the administration of the last dose of study drug, must be reported as follows:

- Death clearly resulting from disease progression should be reported to the Study Monitor/Physician at the next monitoring visit and should be documented in the eCRF in the Statement of Death page. It should not be reported as an SAE.
- Where death is not due (or not clearly due) to progression of the disease under study, the AE causing the death must be reported to the Study Monitor/Physician as an SAE within 24 hours. It should also be documented in the Statement of Death page of eCRF.
- The report should contain a comment regarding the co involvement of PD, if appropriate, and should assign main and contributory causes of death.
- Deaths with an unknown cause should always be reported as an SAE. It should also be documented in the Statement of Death page in the eCRF.

- A post mortem may be helpful in the assessment of the cause of death, and if performed, a copy of the post-mortem results should be forwarded to Sponsor Safety Desk

Deaths occurring after the protocol defined safety follow up period after the administration of the last dose of study drug should be documented in the Statement of Death page. If the death occurred as a result of an event that started after the defined safety follow up period and the event is considered to be due to a late onset toxicity to study drug, then it should also be reported as an SAE.

Death should be considered an outcome and not a distinct event. The event or condition that caused or contributed to the fatal outcome should be reported as the single medical concept. If the cause of death is unknown and cannot be ascertained at the time of reporting, "unexplained death" should be reported as SAE term. If the cause of death later becomes available (e.g., after autopsy), "unexplained death" should be replaced by the established cause of death. The term "sudden death" should only be used for the occurrence of an abrupt and unexpected death due to presumed cardiac causes in a patient with or without pre-existing heart disease, within 1 hour of the onset of acute symptoms or, in the case of an unwitnessed death, within 24 hours after the patient was last seen alive and stable. If the cause of death later becomes available (e.g. after autopsy), "sudden death" should be replaced by the established cause of death.

